9.4. Data Sources

Data for the prospective DAA-PASS cohort will be obtained through abstraction of the participant medical record into the TARGET-HCC database. For selected sites outside of the US, the abstraction will be performed by study site personnel (or designee) while for sites in the US, electronic copies of the participant information will be uploaded for abstraction or imported electronically. Imaging data will be abstracted from local radiological reports. Imaging information will be collected from initial HCC diagnosis through study Follow-up (up to 24 months after the first HCC-free image; the definition of first HCC-free image is defined in Section 9.1.1.).

TPS performed a review of the current participants in TARGET-HCC and it is expected that 15% to 20% of enrolled participants would meet the DAA-PASS inclusion/exclusion criteria.

The abstraction process provides a masking number that is applied to all participant data and used for linking the participant data for analysis purposes. Data are subject to cleaning processes used for TARGET-HCC that evaluate data integrity through a query and review process.

Information regarding the historical cohort data source is described in Section 9.7.9.

9.5. Study Size

9.5.1. Sample Size Justification

Prospective Cohort

A sample size of 600 enrolled participants was planned for the prospective DAA-PASS cohort to capture an expected 122 HCC recurrence events through the 24 months of follow-up based on a 15% annual recurrence rate and 195 expected HCC recurrence events based on a 25% annual recurrence rate. This range of rates is consistent, \pm approximately 5%, with a recently published meta-analysis of HCC recurrence rates by Cabibbo et al⁸ where the 1-year HCC recurrence rate was reported as 20% with 95% CI of 13% to 27%. The sample size was selected based on the expected precision of the estimated HR when the true HR is equal to 1.0 and allows for a conservative rate of censoring from liver transplant or other reasons. The expected precision follows below.

While there are no standards for the timing of DAA therapy following the treatment of HCC, TPS performed a feasibility assessment at HCC study sites on the use of DAAs. The DAA therapy pattern assumed for the sample size evaluation was consistent with what was reported and allowed for 90% (42% by 6 months, an additional 44% by 12 months, and 4% between 12 and 24 months) of participants without recurrence of HCC to be treated through 24 months.

The ability to meaningfully interpret the HR is predicated on the level of precision, quantified by the 95% CI around the effect estimate. As mentioned earlier (see Section 7.2), among other limitations, prior studies had insufficient sample sizes to allow for meaningfully precise estimates (i.e., that could exclude rates greater than two times the rate expected from historical data). Therefore, a key criterion for consideration is that the study should be able to exclude a HR value of 2.0 given a “true” HR of 1.0 (no effect).

Assuming the DAA HR is equal to 1.0, a sample size of 600 participants with an HCC recurrence rate of 15% per 12 months will provide two-sided 95% confidence bounds of 0.66 to 1.61. For a 12-month recurrence rate of approximately 25%, the expected CI bounds of 0.72 to 1.39 would be obtained based on this sample size. Hence, the planned sample size was sufficient to clearly distinguish from a HR of 2.0 if there were no additional HCC recurrence risk related to DAA exposure.

After 2 years of screening and enrollment in DAA-PASS, 30 participants have been enrolled. The primary reason for the low enrollment is that there are very few eligible patients. Most HCC patients are treated for HCV before they are treated for HCC. Assuming the DAA HR is equal to 1.0, a sample size of 70 participants with an HCC recurrence rate of 35% per 12 months will provide two-sided 95% confidence bounds of 0.46 to 2.82. Hence, a sample size of 70 can distinguish from a HR of 3.0 if there is no additional HCC recurrence risk related to DAA exposure. A sample size of 60 participants with an HCC recurrence rate of 35% per 12 months

will provide two-sided 95% confidence bounds of 0.43 to 3.10, and a sample size of 50 participants will yield two-sided 95% confidence bounds of 0.39 and infinity.

Historical Cohort

Information related to the analysis including historical cohort data is described in Section 9.7.9.

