4.8. Study Size

Initially a sample size of 600 enrolled participants was planned for the prospective DAA-PASS cohort to capture an expected 122 HCC recurrence events through the 24 months of follow-up based on a 15% annual recurrence rate or 195 expected HCC recurrence events based on a 25% annual recurrence rate. Due to enrollment challenges, convenience sample sizes between 40 and 70 participants are expected. Based on a meta-analysis from 3 US and European sites^{8,1}, the 1-year HCC recurrence rate is estimated as 35%. Thus, example confidence bounds using the 35% 1-year HCC recurrence rate follow. Assuming the DAA HR is equal to 1.0, a sample size of 70 participants with an HCC recurrence rate of 35% per 12 months will provide two-sided 95% confidence bounds of 0.46 to 2.82. Hence, the convenience sample size of 70 will distinguish from a HR of 3.0 if there is no additional HCC recurrence risk related to DAA exposure. A

sample size of 60 participants with an HCC recurrence rate of 35% per 12 months will provide two-sided 95% confidence bounds of 0.43 to 3.10, and no upper confidence bound is calculable with sample size less than or equal to 50 participants.

The historical cohort will include approximately 400 patients from the ITA.LI.CA database who have HCV and were diagnosed with HCC after 2007 (when the database began to capture follow-up clinical and imaging data), successfully treated for BCLC Stage A HCC with curative therapy, and not treated with DAAs for their HCV infection after HCC diagnosis.

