9.7.1. General Conventions

Descriptive statistical methods for interval-scale measures will include tabulation of count, mean, standard deviation, median, and range. For categorical measures with fixed levels the number of participants will be displayed along with percentages based on participants with available results.

Time to HCC recurrence will be summarized with a life table displaying the numbers of participants at risk entering the time interval, cumulative censored participants, and cumulative proportion with events at the end of the interval. HCC recurrence status will only be evaluated when imaging for HCC is completed. Methods designed to handle interval censoring will be utilized. In addition, if applicable, the cumulative number of participants ongoing or censored by time will be provided.

Descriptive summaries of baseline information, such as demographics, disease characteristics and HCC treatment interventions, will be tabulated. Populations of interest to be displayed in the descriptive summaries are outlined in Section 9.7.2.

All statistical estimates will be reported along with corresponding 95% two-sided CIs. P-values for model parameters will be provided based on Wald statistics.

Unless otherwise specified, all statistical computations will be performed using R software or SAS software (Version 9.4. Copyright © 2012, SAS Institute Inc., Cary, NC).

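### The expected upper confidence bound at 50 or fewer participants is finite, not infinite, and the HR 3.0 statement at 70 is too strong

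*Protocol*

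**What the plan says.** Section 4.8 expects a convenience sample of 40 to 70, and Section 9.5.1 reports 30 enrolled after two years. Precision is described by expected 95% bounds for the DAA hazard ratio when its true value is 1.0 and recurrence is 35% per 12 months:

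- N=70: "will provide two-sided 95% confidence bounds of 0.46 to 2.82"
- N=60: "will provide two-sided 95% confidence bounds of 0.43 to 3.10"
- N=50: "two-sided 95% confidence bounds of 0.39 and infinity"

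Section 4.8 extends the last line to every smaller sample: "no upper confidence bound is calculable with sample size less than or equal to 50 participants". From the N=70 interval, Section 9.5.1 concludes: "Hence, a sample size of 70 can distinguish from a HR of 3.0", provided DAA adds no risk. Section 4.8 makes the same claim with *will* in place of *can*. Neither section says how the bounds were obtained. Section 9.7.1 commits to an interval for every estimate: "All statistical estimates will be reported along with corresponding 95% two-sided CIs".

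**The concern.** Between 60 and 50 participants the upper bound goes from 3.10 to infinity, while the lower bound only moves from 0.43 to 0.39. Losing ten participants should widen the interval by roughly 10% on the log scale, not remove one end of it.

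The pairing is also odd in itself. Section 9.7.1 bases p-values on Wald statistics. In a Cox fit where one exposure state has no usable events, the Wald standard error diverges at both ends, so a single such fit would not give an informative 0.39 alongside infinity.

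With 30 enrolled after two years, 50 or fewer is a plausible final size. Section 9.7 makes the analyses contingent on the final sample size and number of events. A reader could therefore take the statement as a reason not to expect a usable primary interval. At 70, the same reader is told that a hazard ratio of 3.0 will be excluded. The first statement is too pessimistic and the second too optimistic.

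**Working it through.** **1. Scaling the protocol's own intervals.** Implied SE of the log hazard ratio = ln(upper/lower) / (2 × 1.96).

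- N=70: ln(2.82/0.46)/3.92 = 1.813/3.92 = 0.463. Geometric centre √(0.46 × 2.82) = 1.14.
- N=60: ln(3.10/0.43)/3.92 = 1.975/3.92 = 0.504. Geometric centre √(0.43 × 3.10) = 1.15.

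The SE ratio is 0.504/0.463 = 1.089, against √(70/60) = 1.080, so the two intervals follow ordinary root-n scaling. Carried to N=50:

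- from N=70: SE = 0.463 × √(70/50) = 0.547; bounds 1.14 × exp(±1.96 × 0.547) = 0.39 to 3.33
- from N=60: SE = 0.504 × √(60/50) = 0.552; bounds 1.15 × exp(±1.96 × 0.552) = 0.39 to about 3.40

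The protocol's lower bound of 0.39 is reproduced; its upper bound is not. The same scaling gives about 0.34 to 3.8–3.9 at N=40.

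**2. Simulation from the stated inputs.** Taken from the protocol:

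- recurrence of 35% per 12 months and hazard ratio 1.0 (9.5.1)
- DAA uptake of 42% by 6 months, a further 44% by 12 and 4% by 24 (9.5.1)
- imaging at months 3, 6, 9, 12, 18 and 24 (9.2.4)
- the interval in which DAA starts, and all later ones, counted as exposed (Table 3)

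Assumed: exponential recurrence, uptake uniform within each window, a Cox model with DAA as the only covariate and Wald limits, full 24-month follow-up, and a censoring rate. The protocol gives no censoring rate. About 0.29 per year reproduces its expected events at N=600: simulated 122 and 194–195, against 122 and 195 stated in Section 9.5.1.

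Results at 0.29 per year, as ranges over repeated runs:

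| N | Stated | Mean bounds (estimable datasets) | Median bounds | Upper bound < 3.0 |
|---|---|---|---|---|
| 70 | 0.46–2.82 | 0.44–0.45 to 2.77–2.84 | 0.40–0.41 to 2.42–2.50 | 67–68% |
| 60 | 0.43–3.10 | 0.42 to 3.08–3.20 | 0.38 to 2.56–2.68 | about 60% |
| 50 | 0.39–infinity | 0.38–0.39 to 3.55–3.68 | 0.33–0.34 to 2.79–2.90 | 53–55% |
| 40 | none calculable | 0.35 to 4.56–4.78 | 0.30 to 3.2–3.35 | 43–45% |

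At 0.35 per year the mean upper bound at N=50 is about 3.8 and the median about 3.0. The chance of an upper bound below 3.0 is then about 64% at N=70, 50–51% at N=50 and 42% at N=40.

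Every finite stated bound agrees closely with the arithmetic mean of simulated bounds, not with the median. The stated centres of 1.14 and 1.15, when the true value is 1.0, are what averaging right-skewed upper limits would produce.

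**3. How often no bound exists.** At N=50 about 21.7 events are expected, 8.4 of them unexposed. A dataset with no usable unexposed event, which makes the upper bound infinite, occurred in 2 of 40,000 (0.005%) at N=50 and in about 0.07% at N=40. Counting non-estimability in either direction, it stays below 0.1% at N=50 for censoring of 0.29 or 0.35 per year. It also appears very occasionally at N=60, so 50 is not a threshold. A single such dataset is enough to make an average infinite.

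**The case against.** **The cause is not documented.** A reader might infer that the infinity is established as an averaging artefact. The documents do not support that: no simulation is mentioned. At 0.005% per dataset, the chance of at least one infinite replicate is 1 − (1 − 0.00005)^1,000 ≈ 5% in 1,000 replicates and about 39% in 10,000, so averaging would not reliably produce it under full follow-up. The planned model is interval-censored, with about ten covariates and a random centre effect, and could fail more often. This objection stands as to cause. It does not rescue the figure: the stated 70 and 60 intervals match an unadjusted calculation, and on that same basis N=50 is finite.

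**The HR 3.0 sentence follows from its own number.** 2.82 is below 3.0, the section speaks of expected precision, and the ENCePP checklist says that no hypothesis is tested. That is fair, and the sentence contradicts nothing. But an expected bound below 3.0 does not mean that a given study will exclude 3.0.

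**Little turns on it.** Enrolment is set by availability, the infinity understates precision and so cannot reassure falsely, and the reported interval will come from the data. This limits the importance but does not make the figure right.

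**The June 2021 cutoff.** A reader might infer specific, lower probabilities from shortened follow-up. The direction is plausible, but the protocol gives no accrual pattern, so no such percentage can be derived from it.

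**Conclusion.** The statements in Sections 4.8 and 9.5.1 about 50 or fewer participants are wrong as descriptions of expected precision. On the protocol's own scaling, the N=50 upper bound is about 3.3 to 3.4. Across assumed censoring of 0.29 to 0.35 per year, simulation puts its mean at about 3.6 to 3.8 and its median at about 2.8 to 3.0. At N=40 the mean is about 4.5 to 4.8 and the median about 3.2 to 3.4. More than 99.9% of simulated N=50 datasets give a finite bound. Averaging over rare non-estimable replicates is the probable explanation, but it is inferred.

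The claim about a hazard ratio of 3.0 is too strong: over the same censoring range, the upper bound falls below 3.0 in about 64–68% of simulated studies at N=70, 50–55% at N=50 and 42–46% at N=40.

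The scaling result needs only the stated intervals. The simulated figures rest on assumed censoring, full 24-month follow-up and no covariates; the planned adjusted model will be less precise. Nor does a finite bound make N=50 informative: the corrected intervals remain wide. The point is moderate and worth correcting, because it misstates the primary analysis within the expected sample range.

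**What to change.** In Sections 4.8 and 9.5.1:

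1. Replace the infinite and non-calculable upper bounds with finite bounds for N=40, 50, 60 and 70, given as medians or as clearly labelled means, together with the share of non-estimable datasets at each N.
2. Replace the statement that 70 participants will or can distinguish a hazard ratio of 3.0 with the probability that the upper bound is below 3.0 at each N.
3. State how the bounds were derived and the censoring and follow-up assumed. If the June 2021 cutoff is brought in, give the accrual assumption with a range.
4. Say that these figures are unadjusted, if they are, and that the covariate-adjusted model will be less precise.

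The cost is one recalculation, or a re-summary if the bounds came from simulation, and a text edit in two sections. Design, data collection and the planned analysis do not change.

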9.6. Data Management

Data management activities for the prospective cohort will be performed in accordance with TPS procedures. A separate Data Management Plan (DMP) and other design documents describing study-specific information will be generated and finalized prior to initiating data management activities for DAA-PASS.

All data for the prospective DAA-PASS cohort will be collected, processed, and stored centrally via an electronic data capture system by Sponsor personnel or their designee. Data management activities will be performed by TPS or their designee. Coding of data will be performed as appropriate using the Medical Dictionary for Regulatory Activities (MedDRA) and the World Health Organization (WHO) Drug dictionaries.

In addition, copies of the raw images used for HCC assessment in the prospective cohort will be obtained and stored centrally.

Information related to the historical cohort is described in Section 9.7.10.

9.7. Data Analysis

The analyses below will be generated under ideal circumstances, though in practice, they may be contingent according to the final sample size, its distribution among subpopulations determined by important covariates, and the final number of recurrence events observed. A separate Statistical Analysis Plan (SAP) will also be generated that will include further details of the planned analyses.

The analysis for the Primary Objective provides an estimate of the HR associated with recurrence of HCC associated with DAA therapy relative to no DAA therapy. The planned analyses use a proportional hazards model with DAA exposure included in the model as a time-dependent variable. Details of the analysis methods are provided below, including the approach to adjust for potential bias and sensitivity analyses.

The analysis for Secondary Objective A will evaluate the adjusted incidence of HCC recurrence using data from the DAA-PASS, as described in Section 9.7.8.

Analyses for Secondary Objectives B and C will repeat those of the Primary Objective and Secondary Objective A, incorporating data from the historical cohort as part of the non-DAA exposure condition. A description of this cohort is provided in Section 9.7.9 and the analyses are described in Section 9.7.8 and Section 9.7.9.

Furthermore, an additional descriptive analysis for the Exploratory Objective will be performed to characterize the cumulative risk of HCC recurrence in the historical cohort only (see Section 9.7.10).

9.7.1. General Conventions

Descriptive statistical methods for interval-scale measures will include tabulation of count, mean, standard deviation, median, and range. For categorical measures with fixed levels the number of participants will be displayed along with percentages based on participants with available results.

Time to HCC recurrence will be summarized with a life table displaying the numbers of participants at risk entering the time interval, cumulative censored participants, and cumulative proportion with events at the end of the interval. HCC recurrence status will only be evaluated when imaging for HCC is completed. Methods designed to handle interval censoring will be utilized. In addition, if applicable, the cumulative number of participants ongoing or censored by time will be provided.

Descriptive summaries of baseline information, such as demographics, disease characteristics and HCC treatment interventions, will be tabulated. Populations of interest to be displayed in the descriptive summaries are outlined in Section 9.7.2.

All statistical estimates will be reported along with corresponding 95% two-sided CIs. P-values for model parameters will be provided based on Wald statistics.

Unless otherwise specified, all statistical computations will be performed using R software or SAS software (Version 9.4. Copyright © 2012, SAS Institute Inc., Cary, NC).

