9.2.4. Follow-up

The Follow-up period will continue for up to 24 months from Enrollment/Baseline for all participants. Imaging will be performed per standard of care^{10,11}, as follows (see Table 2):

- Every 3 months for the first 12 months after Enrollment/Baseline
- At 18 and 24 months after Enrollment/Baseline

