9.3. Variables

The prospective DAA-PASS cohort will include information on participant demographics, laboratory values, medical history events, concomitant medication use (including hepatotoxic medications), alcohol use, staging of liver disease and HCC (including but not limited to Child-Pugh score, Model for End Stage Liver Disease [MELD] score, performance status, and BCLC stage), HCC treatment intervention(s) and response, tumor assessments, additional liver imaging information, prior and subsequent HCV treatment (including IFN), DAA therapy, and virologic response data.

The data for the prospective DAA-PASS cohort include imaging collection and details of DAA therapy from the TARGET-HCC database. The database includes information on participant demographics, laboratory values, comorbid liver conditions (including but not limited to HCV status), medical history events (including adverse events), concomitant medication use, HCV treatment history, HCC staging information, tumor assessment and response, HCC treatment history, and additional liver imaging information.

The model will include the following baseline covariates as available: alpha-fetoprotein (AFP) level, albumin level, platelet count, MELD score, age in years, gender, diabetes status, alcohol use/AUDIT score ≥ 7 , HCC treatment modality, and study centre (see Section 9.7.6.2).

The historical cohort will include similar data extracted from the ITA.LI.CA database (where available). Information related to the variables collected in the historical cohort is described in Section 9.7.9.

Definition of HCC Recurrence

The objectives are based on the analysis of early HCC recurrence (see Section 9.1.1) as indicated on imaging following Enrollment/Baseline (date of first HCC-free image; see Section 9.1.1). Periodic screening for HCC recurrence will rely on conventional imaging-based evaluations. HCC recurrence is defined (see Section 9.1.1) as having evidence of enhancing lesions suggestive of new HCC on imaging after successful treatment of HCC. The onset of HCC recurrence will be assumed to occur during the time interval between a previous negative imaging evaluation and the subsequent positive imaging evaluation. The time of onset will thus be interval-censored instead of being known precisely. Participants will be considered to have an event if they have an HCC recurrence in an interval as demonstrated by imaging.

DAA exposure

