9.7.3. DAA Exposure as Time-Varying Exposure

Individual participants in the prospective DAA-PASS cohort can contribute person-time to both DAA exposure and no DAA exposure. DAA exposure is a function of time. The no DAA exposure starts at the enrollment/baseline image (Index Date; i.e., successful treatment of HCC) and continues until the participant has an event (i.e., HCC recurrence), initiates DAA therapy, completes the study without initiating DAA therapy, or is otherwise censored. The DAA exposure starts at the first date a DAA is initiated and continues until the participant has an event, completes the study, or is otherwise censored. Participants are censored in whichever exposure type they are in (no DAA exposure or DAA exposure) if they receive IFN treatment, a liver transplant, die, withdraw from the study, or are otherwise removed or lost to follow-up while enrolled in DAA-PASS. Participants that receive DAA therapy starting on the date of Enrollment/Baseline only contribute person-time to DAA exposure and participants that never receive DAA therapy only contribute person-time to the no DAA therapy exposure person-time. The completion of the study is defined by obtaining imaging corresponding to the 24-month follow-up assessment. Note that participants who received a liver transplant while enrolled in DAA-PASS will continue to be followed up to 24 months from Enrollment/Baseline.

Additional information on DAA therapy will be collected including, as available, the DAA prescribed, duration of dosing and planned duration, and SVR response. These will be summarized descriptively.

9.7.4. Coding Convention for HCC Recurrence and DAA as Time-Varying Exposure for the Primary Analysis

This section provides additional details on the coding of the HCC recurrence endpoint for analysis. The primary model of time of onset is based on interval-censoring as outlined in Section 9.7.6.1. The intervals between imaging evaluations are not required to have a fixed length and a participant with a missed visit would simply experience an extended interval -- assuming they have a later follow-up assessment. For the analysis, individuals will have a record of an event or not corresponding to each available interval of no DAA exposure or DAA exposure. The table below provides some examples of participant data where t_{i0} is baseline and t_{ij} for $j = 1$ to n_i represent sequential imaging assessment times for the i^{th} participant:

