9.7.8. Evaluation of Incidence of HCC Recurrence (Secondary Objectives A and C)

Secondary Objectives A and C are to evaluate the adjusted incidence of recurrence of HCC using the endpoint of the number of events.

An analysis approach based on inverse-probability of censoring weighted averages (IPCW) as outlined in Satten and Datta¹⁶ will be used to obtain an adjusted estimate of the cumulative risk and expected total events for the prospective cohort under the assumption that none of the participants had received DAA. For this analysis, a proportional hazards model of the time-to-censoring event of the non-DAA HCC exposure caused by the start of DAA exposure using the primary analysis covariates will be performed. The model parameters will give individual participants IPC weights in order get an adjusted estimate of the cumulative risk and total events had participants not gotten DAA exposure.

This estimate of risk will be compared to the actual observed risk in the cohort (estimated by the complement of the Kaplan-Meier estimator) to assess the impact of DAA use on HCC recurrence in the prospective cohort. The results will be presented at follow-up time points of 3, 6, 9, 12, 18, and 24 months.

In order to obtain CIs for the estimated risk difference and differences in number of HCC recurrence events at each of the time points, bootstrapping will be used to resample participants from the entire prospective population.

The estimated and actual cumulative event counts will be displayed at the indicated time points. Survival and cumulative event curves will be displayed in figures. Information on significance of the modeling parameters used in the IPCW model will be provided.

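### Section 9.7.8 reads right-censored Kaplan-Meier and IPCW curves at the scheduled imaging months, although 9.3 and 9.7.1 call recurrence interval-censored; absolute risks come out too low when images are late or missed

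*Protocol*

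**What the plan says.** Protocol 9.3, under the definition of recurrence, places onset between the last negative and the first positive image and concludes: "The time of onset will thus be interval-censored instead of being known precisely". Section 9.7.1, in the paragraph on time to recurrence, says "Methods designed to handle interval censoring will be utilized"; the abstract (4.9) says the same. Sections 9.7.4 to 9.7.6.1 carry this into the primary Cox model.

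Section 9.7.8 covers the cumulative risk and event counts of Secondary Objectives A and C. The observed risk is "estimated by the complement of the Kaplan-Meier estimator". The risk had nobody received DAA is an IPCW estimate, taken from a reference that presents Kaplan-Meier as such a weighted average. On timing: "The results will be presented at follow-up time points of 3, 6, 9, 12, 18, and 24 months". The section gives no interval-censored version and no rule for the date an event receives. Section 9.7.9 applies the same approach to the pooled cohorts for Secondary Objective C.

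The imaging schedule in 9.2.4 is "Every 3 months for the first 12 months after Enrollment/Baseline" and "At 18 and 24 months after Enrollment/Baseline". Section 9.7.4 does not expect strict adherence: "The intervals between imaging evaluations are not required to have a fixed length", and a missed visit simply lengthens the interval.

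**The concern.** The estimator named in 9.7.8 does not fit the data type that 9.3 and 9.7.1 describe. Kaplan-Meier treats the recorded date as the event date. If that is the date of the detecting image, detection can only follow onset, so one minus Kaplan-Meier cannot, apart from sampling error, exceed the true cumulative onset.

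Reading the curve at the nominal imaging months makes it sensitive to small delays. An image a few days after month 3 carries the recurrences of the whole preceding interval, and none of them count at month 3. An early image loses only the onsets between it and the nominal month. Absolute risks and event counts, the stated endpoints of Secondary Objectives A and C, would be too low, and the bootstrap intervals would not show it because resampling reproduces the same shift.

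**Working it through.** **The plan's own figures.** The protocol gives no number for this estimator. Its only event counts, 122 and 195 among 600 (9.5.1), depend on a censoring rate it does not state. Without censoring, 600 × (1 − 0.85²) = 166.5 and 600 × (1 − 0.75²) = 262.5. A common censoring rate of 0.35 per year yields 122 and 195.1. The two counts agree with each other and are not in dispute.

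**Inputs.** Recurrence of 35% per 12 months (9.5.1), assumed exponential; images at 3, 6, 9, 12, 18 and 24 months (9.2.4); the same reporting months (9.7.8). Assumed, because the protocol gives none: events dated at the detecting image, the scatter of image dates, the share of missed images, and no censoring other than at the last image (9.7.5).

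**True risk.** F(t) = 1 − 0.65^(t/12) gives 10.2, 19.4, 27.6, 35.0, 47.6 and 57.7% at the six months.

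**Hand check.** With small symmetric scatter, about half the images due at a given month fall after it. The shortfall there is about half the risk gained in the preceding interval, ½[F(t_k) − F(t_(k−1))]:
- month 3: 10.2/2 = 5.1 points
- month 6: (19.4 − 10.2)/2 = 4.6
- month 9: (27.6 − 19.4)/2 = 4.1
- month 12: (35.0 − 27.6)/2 = 3.7
- month 18: (47.6 − 35.0)/2 = 6.3

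At month 24 the approximation is too large, because negative last images are themselves censored around that date.

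**Simulation** (1,000,000 participants per row; one minus Kaplan-Meier on detection dates, %):

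| Images | 3 | 6 | 9 | 12 | 18 | 24 |
|---|---|---|---|---|---|---|
| True onset | 10.2 | 19.4 | 27.6 | 35.0 | 47.6 | 57.7 |
| On schedule, none missed | 10.2 | 19.3 | 27.6 | 35.0 | 47.6 | 57.7 |
| On schedule, 10% missed | 9.2 | 18.4 | 26.7 | 34.2 | 46.4 | 57.8 |
| Uniform within ±0.25 month | 4.9 | 14.7 | 23.4 | 31.2 | 41.2 | 54.1 |
| Normal, SD 0.5 month | 4.5 | 14.2 | 23.0 | 30.9 | 40.9 | 53.9 |
| Uniform within ±1 month | 4.3 | 14.0 | 22.8 | 30.7 | 40.8 | 53.8 |
| SD 0.5 month, 10% missed | 4.0 | 13.3 | 22.1 | 30.0 | 40.1 | 54.0 |

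The three rows with scatter alone fall short by 3.7 to 6.8 points. Because the readout sits on the imaging month, a week of scatter does nearly as much as a month. Missed images without scatter cost up to 1.2 points here and up to 1.4 across repeated runs. At 15% per year with SD 0.5 month the shortfall is 2.0 to 3.5 points. An interval-censored piecewise-exponential fit to the half-month-scatter data, with or without missed images, recovered the true risks to about 0.1 point.

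**Event counts.** If counts are risk times cohort size, 4 to 7 points among 70 participants is 70 × 0.04 = 2.8 to 70 × 0.07 = 4.9 events.

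**Observed minus no-DAA risk.** DAA uptake as in 9.5.1 (42% by 6 months, a further 44% by 12, 4% more by 24), no confounding, SD 0.5 month, 10% missed. At a hazard ratio of 1 the difference stays within 0.3 point of zero. At a hazard ratio of 2:

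| Month | 3 | 6 | 9 | 12 | 18 | 24 |
|---|---|---|---|---|---|---|
| True difference (points) | 1.0 | 3.3 | 6.6 | 10.2 | 15.6 | 17.4 |
| Estimated | 0.3 | 1.7 | 4.2 | 7.7 | 12.2 | 15.2 |

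**The case against.** The sentence in 9.7.1 sits beside the life table, the interval coding of 9.7.4 is headed as being for the primary analysis, and 9.7.8 is the specific text for Secondary Objectives A and C. The SAP, which is not available here, may fix the event date; if events are assigned to the nominal visit and no image is missed, the bias disappears. That stands, and it makes the size conditional. It does not remove the inconsistency, because the protocol itself names a right-censored estimator for an endpoint it has called interval-censored.

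Precision also limits the practical weight. At 70 participants the 95% half-width of a single proportion, 1.96 × √(p(1 − p)/70), is 7.1 points at p = 0.102, 11.2 at 0.35 and 11.6 at 0.577, more than most of the shortfalls. Those widths describe random error, however, and this shift is systematic.

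Three stronger readings are tempting and not supported:
- That risk is understated at every time point whatever happens. With images on schedule the error is zero, and the protocol gives no imaging window from which to derive another value.
- That Secondary Objective C will show a false early excess in the prospective cohort. This needs an assumed historical schedule (6-monthly, say) and a contrast that 9.7.8 and 9.7.9 do not clearly specify. With that schedule and historical patients in both curves, a simulated contrast at a hazard ratio of 1 was 0.0 at all six months. A gap of 3.0 to 4.5 points through month 12 appeared only when prospective participants alone were set against the pooled no-DAA curve. Section 9.9.2 already concedes that assessment timing may differ.
- That the damage falls on the early months the study is about. The protocol defines early recurrence as any recurrence in follow-up, up to 24 months (9.1.1).

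**Conclusion.** The concern holds in a conditional form. Section 9.7.8 conflicts with 9.3 and 9.7.1. If events are dated at the detecting image, absolute risks and event counts are too low whenever images fall after the nominal month or are missed. At 35% per year the shortfall is about 4 to 7 points with scatter of one week to one month, 0 to about 1.4 points with 10% missed and the rest on schedule, and zero with all images on schedule. Scatter and missed-image rates are assumptions.

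The within-cohort contrast is close to unbiased under no effect and diluted under harm, the unfavourable direction for a safety study. In Secondary Objective C, different image timing in the historical cohort could add differential error, of a size the documents do not allow one to derive. The primary Cox model is not affected by this point.

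**What to change.** In 9.7.8, replace both right-censored curves with one interval-censored estimator: either a discrete-time estimate grouped by scheduled imaging interval, or a piecewise-exponential interval-censored model. Apply the DAA-start weights per interval, and run the participant bootstrap on that grouped or parametric estimator. A weighted Turnbull estimate is less suitable: it is not routine software, and the ordinary bootstrap is not generally valid for it when image dates vary continuously.

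Use the same estimator for the historical cohort where the date of the last negative image exists. Section 9.7.9 says those data were abstracted at diagnosis and treatment and then at recurrence, so that date may be unavailable; where it is, report the limitation.

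The cost is a change to one section, slightly more programming and coarser time resolution. No additional data collection is needed in the prospective cohort.
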